21. DATA NOT SUMMARIZED OR PRESENTED

The list of data not summarized or presented is available in the Master COV-01 SAP.

APPENDIX 1 MEDDRA ALGORITHMIC APPROACH TO ANAPHYLAXIS

The SMQ anaphylactic reactions consists of three parts:

- A narrow search containing PTs that represent core anaphylactic reaction terms:

Category A

- Anaphylactic reaction
- Anaphylactic shock
- Anaphylactic transfusion reaction
- Anaphylactoid reaction
- Anaphylactoid shock
- Circulatory collapse
- Dialysis membrane reaction
- Kronis syndrome
- Shock
- Shock symptom
- Type I hypersensitivity

- A broad search that contains additional terms that are added to those included in the narrow search. These additional terms are signs and symptoms possibly indicative of anaphylactic reaction and categorized in B, C or D.

Category B (Upper Airway/ Respiratory)

- | | | |
|---|--|--|
|  Acute respiratory failure |  Irregular breathing |  Respiratory failure |
|  Asthma |  Laryngeal dyspnea |  Reversible airways obstruction |
|  Bronchial oedema |  Laryngeal oedema |  Sensation of foreign body |
|  Brochospasm |  Laryngospasm |  Sneezing |
|  Cardio-respiratory distress |  Laryngotracheal oedema |  Stridor |
|  Chest discomfort |  Mouth swelling |  Swollen tongue |
|  Chocking |  Nasal obstruction |  Tachypnoea |
|  Chocking sensation |  Oedema mouth |  Throat tightness |
|  Circumoral oedema |  Oropharyngeal spasm |  Tongue oedema |
|  Cough |  Oropharyngeal swelling |  Tracheal obstruction |
|  Cyanosis |  Respiratory arrest |  Tracheal oedema |
|  Dyspnoea |  Respiratory distress |  Upper airway obstruction |
|  Hyperventilation |  Respiratory dyskinesia |  Wheezing |
-

Category C (Angioedema/ Urticaria/ Pruritus/ Flush)

- | | | |
|---------------------------------------|--|---|
|  Allergic oedema |  Injection site urticaria |  Rash |
|  Angioedema |  Lip oedema |  Rash erythematous |
|  Erythema |  Lip swelling |  Rash generalized |
-

CCI

PPD

Version Number: Amendment 2, v1.0
Version Date: 28-Jul-2021

CCI

Category C (Angioedema/ Urticaria/ Pruritus/ Flush)

- | | | |
|--|--|---|
|  Eye oedema |  Nodular rash |  Rash pruritic |
|  Eye pruritus |  Ocular hyperaemia |  Skin swelling |
|  Eye swelling |  Oedema |  Swelling |
|  Eyelid oedema |  Periorbital oedema |  Swelling face |
|  Face oedema |  Pruritus |  Urticaria |
|  Flushing |  Pruritus allergic |  Urticaria papular |
|  Generalised erythema |  Pruritus generalised | |

Category D (Cardiovascular / Hypotension)

- | | | |
|--|--|---|
|  Blood pressure decreased |  Cardiac arrest |  Diastolic hypotension |
|  Blood pressure diastolic decreased |  Cardio-respiratory arrest |  Hypotension |
|  Blood pressure systolic decreased |  Cardiovascular insufficiency | |

- An algorithm approach which combines a number of anaphylactic reaction symptoms in order to increase specificity will be used for this sub-protocol. A potential anaphylactic reaction is defined meeting at least one of the following criteria where the different terms occur on either the same day as when an injection was administered or one day after:
 - A narrow PT from Category A;
 - A PT from Category B AND a PT from Category C;
 - A PT from Category D AND (a PT from Category B OR a term from Category C).

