14. EXPOSURE TO STUDY DRUG

Patients randomized to sub-protocol COV-01-005

Patients randomized to zilucoplan plus standard of care (SoC) and placebo plus SoC treatment arms of COV-01-005 sub-protocol will receive a single daily dose of 32.4 mg of the study drug (prefilled syringes containing 0.81 mL of zilucoplan or placebo, as appropriate) administered by subcutaneous (SC) injection in the abdomen (preferred site), thigh or upper arm.

The daily administration of study treatment will start on Day 1 (baseline) and continue to Day 14 or until hospital discharge, whichever occurs first. If the patient is discharged before 14 days of treatment, zilucoplan or placebo should be stopped at time of discharge or 24 hours before discharge.

Reason for dose modification of study drug (i.e. dose interrupted or drug withdrawal) will be captured in the *Exposure* page of the eCRF.

Patients included in the control arm of COV-01-005 sub-protocol who were randomized to the placebo plus SoC group of a sub-protocol other than COV-01-005

It is to be noted that the planned duration of exposure to a study drug, planned frequency of administration of the study drug, and planned route of administration of the study drug will vary from one sub-protocol to the other, but similar information as for COV-01-005 sub-protocol will be captured on the *Exposure* page of the eCRF of these other sub-protocols.

Exposure to study drug

The exposure to study drug will be summarized by treatment arm (breaking down the placebo plus SoC arm by sub-protocol) based on the safety analysis set as follows:

[figure not shown]
- Duration of exposure:
 - Duration of exposure (days) as a continuous variable;
 - Duration of exposure (days) as a categorical variable: 1 to 3, > 3 to 7, > 7 to 14, and > 14;
 - Total number of doses received as a continuous variable, where the total number of doses received is defined as the total number of doses received by each patient, not the total number of doses received across all patients.

CCI

PPD

Version Number: Amendment 2, v1.0
Version Date: 28-Jul-2021

CCI

- Dose modifications:
 - Number and percentage of patients with at least one interrupted dose;
 - Number and percentage of patients with at least one dose interruption by reason for dose interruptions:
 - Adverse events;
 - Other.
 - Total number of dose interruptions as a continuous variable, where the total number of dose interruptions is defined similarly to the total number of doses received;

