17.1. ADVERSE EVENTS

17.1.1. ADVERSE EVENTS OF SPECIAL INTEREST

The following are defined as adverse events of special interest (AESIs) for this sub-protocol and will be identified based on pre-defined coded preferred terms (PTs), high-level terms (HLTs, and/or system organ class:

- Anaphylactic reactions (Medical Dictionary for Regulatory Activities [MedDRA] algorithmic approached; refer to [Appendix 1](#));
- Serious anaphylactic reactions (MedDRA algorithmic approached; refer to [Appendix 1](#));
- Hypersensitivity reactions (standardized MedDRA query [SMQ] – narrow scope; refer to [Appendix 2](#));
- Serious hypersensitivity reactions (SMQ – narrow scope; refer to [Appendix 2](#));
- Infections (MedDRA system organ class of ‘Infections and infestations’);
- Serious infections (MedDRA system organ class of ‘Infections and infestations’);
- Neisseria infections (MedDRA high level term [HLT] of ‘Neisseria infections’);
- Serious Neisseria infections (HLT of ‘Neisseria infections’);
- Drug related hepatic disorders (SMQ – comprehensive search; refer to [Appendix 3](#)), excluding the ‘Liver neoplasms, benign (incl. cysts and polyps)’ and ‘Liver neoplasms, malignant and unspecified’ sub-SMQs.

A summary of treatment-emergent (refer to Master COV-01 SAP Section 17.1) AESIs overall and by AESI category and preferred term (PT) will be prepared by treatment arm for patients randomized to COV-01-005 only. Should a patient experience multiple events within an AESI category or PT, the patient will be counted only once for that AESI category or PT. The risk difference of the overall incidence rates of having any treatment-emergent AESI between the treatment arms will be presented along with its two-sided 95% Wald CI. A listing of all AESIs will be provided for patients randomized to COV-01-005 only.

CCI

PPD

Version Number: Amendment 2, v1.0
Version Date: 28-Jul-2021

CCI

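### The zilucoplan anaphylaxis algorithm does not say that combined terms must relate to the same injection, so under daily dosing a literal reading accepts terms up to 14 days apart

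*SAP*

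**What the plan says.** COV-01-005 SAP Section 17.1.1 lists the adverse events of special interest (AESIs), to be identified from pre-defined coded terms. Two of the categories are anaphylactic reactions and "Serious anaphylactic reactions (MedDRA algorithmic approached; refer to" Appendix 1. They are tabulated by arm for patients randomized to COV-01-005 only, and all AESIs in these patients are listed.

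Appendix 1 gives the algorithm. It says the approach "combines a number of anaphylactic reaction symptoms in order to increase specificity". Then: "A potential anaphylactic reaction is defined meeting at least one of the following criteria", with the timing condition "where the different terms occur on either the same day as when an injection was administered or one day after". The criteria are:

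- one Category A term;
- a respiratory term (Category B) together with a skin or swelling term (Category C);
- for cardiovascular terms, "A PT from Category D AND (a PT from Category B OR a term from Category C").

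Category B (respiratory) includes cough, dyspnoea, tachypnoea, respiratory distress and "Acute respiratory failure". Category C includes rash, pruritus and oedema. Category D includes hypotension and cardiac arrest.

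On dosing, COV-01-005 SAP Section 14 says: "The daily administration of study treatment will start on Day 1 (baseline) and continue to Day 14 or until hospital discharge". Sub-protocol COV-01-005 Section 5.1 confirms one subcutaneous injection a day.

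**The concern.** Combining terms raises specificity only if the terms belong to one clinical episode. The timing condition is the only part of the rule that could enforce this, and it links the terms to an injection without saying that it must be the same one. With a single dose, or doses far apart, that would matter little. With an injection every day, the one-day windows join into a single window covering the whole treatment period.

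The population makes this relevant. Several Category B terms are manifestations of COVID-19, and Master Protocol Section 8.4.7 has disease-related signs and symptoms reported as adverse events where appropriate. All patients in this sub-protocol also receive antibiotic prophylaxis (sub-protocol Section 5.6), a plausible separate source of a Category C rash.

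No adjudication step is described, and sub-protocol Section 4.1.1.2 defines no AESI, so this algorithm is the operative definition. At stake is whether the two anaphylaxis rows can be read as counts of plausible reactions.

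**Working it through.** The plan states no figure for this rule, so there is none to reproduce. The check enumerates days.

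**Inputs**

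- A term qualifies on an injection day or the day after (Appendix 1).
- One injection a day from Day 1, 14 at most (SAP Section 14).
- Assumption: a term's day is its start day.

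**Qualifying days.** With k uninterrupted daily injections on Days 1 to k, the qualifying days are Days 1 to k + 1. For k = 14 that is Days 1 to 15, with no gaps. The largest separation between two qualifying terms is (k + 1) − 1 = k days: 14 days for the full course, 7 days for 7 injections.

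**Example.** Cough starting on Day 2 and hypotension starting on Day 12 both fall on injection days. Read literally, the pair meets the criterion of D with B, although the terms are 10 days apart.

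**Comparison with a linked rule.** The literal rule accepts all (k + 1)² ordered pairs of qualifying days. A rule requiring both terms on the day of, or the day after, the same injection accepts k + 1 same-day pairs and 2k adjacent-day pairs, so 3k + 1.

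| Injections (k) | Literal rule | Linked rule | Share kept |
|---|---|---|---|
| 14 | 15² = 225 | 15 + 28 = 43 | 19% |
| 7 | 8² = 64 | 8 + 14 = 22 | 34% |
| 3 | 4² = 16 | 4 + 6 = 10 | 63% |
| 1 | 2² = 4 | 2 + 2 = 4 | 100% |

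For the full course the literal rule accepts 225 / 43 = 5.2 times as many day-pairs.

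**Sensitivity.** Reading these shares as proportions of coincidental pairs assumes independent onset, uniform over the qualifying days. If onset is instead front-loaded (geometric, 10%, 20% or 30% per day, 14 injections), the linked rule keeps 22%, 31% or 43%, so it removes 57% to 78%. If respiratory and cardiovascular events cluster in time, it removes less. These onset patterns are assumptions; the documents give none.

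**Other timing filters.** Master SAP Section 17.1 requires a treatment-emergent event to start or worsen on or after the first dose. This drops unchanged pre-dose symptoms but does not link terms to each other. No such link was found elsewhere in the Master SAP, the COV-01-005 SAP or the sub-protocol.

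**The case against.** The strongest objection is that the sentence can be read collectively: the different terms, together, around one injection. The word *each* is not in the text, and on this reading the Day 2 and Day 12 example fails. That stands as a possible reading. But the text names neither the same injection nor a maximum interval, and a programmer could implement either version.

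Other limits also stand:

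- The condition is not empty. Adverse events are collected to the final follow-up visit (Master Protocol Section 8.4.1), and the rule excludes terms starting more than a day after the last injection. It is redundant only during continuous dosing.
- Early discharge or stopping shortens the window.
- Appendix 1 says *potential*. The row labels in Section 17.1.1 drop that word, but a placebo column and a listing of AESIs accompany them.
- Investigators record a diagnosis in preference to separate signs where possible (Master Protocol Appendix 4), which reduces stand-alone cough or dyspnoea reports.
- Much of the overlap with COVID-19 and intensive-care events comes from the category lists themselves. Same-day respiratory failure and hypotension would still be flagged under a linked rule, and Category A accepts shock or circulatory collapse as single terms.
- The rule applies alike to zilucoplan and its placebo, so it does not favour an arm by design.

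**Conclusion.** The point holds as a gap in the wording with a real consequence under daily dosing. Read literally, Appendix 1 accepts combined terms up to 14 days apart in a full course, contrary to its stated aim of greater specificity. The loss of specificity falls on the anaphylaxis and serious-anaphylaxis rows, in both arms. These are descriptive rows in a terminated sub-protocol with 108 randomized patients (COV-01-005 SAP Section 16). Efficacy is untouched.

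Three stronger conclusions might be inferred, and the documents do not support them.

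- **That the rows would consist mostly of coincidental events, or that a number of false flags can be given.** The documents contain no event rates. With P(flag) = P(B) × P(C or D) + P(not B) × P(C and D) and independence, assumed rates of B 10%, C 2%, D 5% give 0.10 × 0.069 + 0.90 × 0.001 = 0.8%, about 1 of 108. Rates of B 40%, C 10%, D 15% give 0.40 × 0.235 + 0.60 × 0.015 = 10.3%, about 11 of 108. That spread is too wide to be informative, and it is the total flagged, not the excess over a linked rule.
- **That the any-AESI risk difference is distorted.** That composite also contains all infections and a broad hepatic search, and no effect of the timing rule on it is shown.
- **That the report would attribute anaphylaxis to a drug that caused none.** The placebo comparison, the listing and the word *potential* all stand against this.

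The day-pair shares are illustrations under stated onset assumptions, not forecasts.

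**What to change.** In Appendix 1, require the combined terms (B with C; D with B or C) to start on the day of, or one day after, the same injection. Under uninterrupted daily dosing this equals starting on the same or consecutive days as each other. After a missed dose the two can differ (with injections on Days 1 and 3, Days 2 and 3 are consecutive but share no injection), so the SAP should use the same-injection wording. Leave Category A unchanged. Label the rows as potential, and potential serious, anaphylactic reactions. In the AESI listing already planned, show the onset day of each contributing term and the last injection date.

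The cost is one sentence, a row label and a date comparison in the program. Event start dates and dosing dates are already used in Master SAP Section 17.1 and COV-01-005 SAP Section 14.1. The downside is small: a reaction whose components are recorded more than a day apart would be missed unless it was coded to a Category A term. Same-day pairs caused by the disease will still be flagged, and the listing lets a reader judge them.

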APPENDIX 2 SMQ OF HYPERSENSITIVITY REACTIONS (NARROW SCOPE)

Preferred Term

- Administration site hypersensitivity
 - Documented hypersensitivity to administered product
 - Drug hypersensitivity
 - Hypersensitivity
 - Infusion related hypersensitivity reaction
 - Infusion site hypersensitivity
 - Injection site hypersensitivity
 - Type I hypersensitivity
 - Type II hypersensitivity
 - Type IV hypersensitivity
-

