### Hypersensitivity Reactions

As hypersensitivity reactions have been observed for monoclonal antibodies as a class, these events are considered AESI for this study. Investigators will report all diagnoses, or signs and symptoms when diagnoses cannot be determined, that are consistent with hypersensitivity reactions, regardless of causality, within 24 hours from the time of study drug administration.

Investigators will report hypersensitivity reactions that occur after 24 hours, only if the reactions are suspected to be related to study drug.

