APPENDIX 1 HYPERSENSITIVITY REACTIONS

Preferred Term

- Administration site hypersensitivity
 - Documented hypersensitivity to administered product
 - Drug hypersensitivity
 - Hypersensitivity
 - Infusion related hypersensitivity reaction
 - Infusion site hypersensitivity
 - Injection site hypersensitivity
 - Type I hypersensitivity
 - Type II hypersensitivity
 - Type IV hypersensitivity
-

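### In the COV-01-005 SAP, hypersensitivity AESIs rest on a ten-term list, so isolated angioedema, urticaria and similar allergic terms fall outside both allergy-related AESI categories

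*SAP*

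**What the plan says.** **How AESIs are found in COV-01-005.** COV-01-005 SAP Section 17.1.1 states that AESIs are "identified based on pre-defined coded preferred terms (PTs), high-level terms (HLTs, and/or system organ class". Two of its categories concern hypersensitivity: "Hypersensitivity reactions (standardized MedDRA query [SMQ] – narrow scope; refer to [Appendix 2" and "Serious hypersensitivity reactions (SMQ – narrow scope; refer to [Appendix 2". Both point to Appendix 2, headed "APPENDIX 2 SMQ OF HYPERSENSITIVITY REACTIONS (NARROW SCOPE", which is a closed list of ten preferred terms.

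**What else the same SAP lists.** Appendix 1 gives the anaphylaxis algorithm. Category A holds the core anaphylaxis terms. Category B covers the airway and Category D the circulation. The skin and oedema group is headed "Category C (Angioedema/ Urticaria/ Pruritus/ Flush". A Category A term qualifies by itself. A Category C term qualifies only together with a Category B or Category D term. The terms must fall on an injection day or the day after it.

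**What is reported.** AESIs are tabulated overall, by category and by preferred term, for patients randomized to COV-01-005 only. One risk difference, for having any treatment-emergent AESI, is shown with a confidence interval.

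**What the sub-protocol asks of investigators.** Section 4.1.1.2 of the COV-01-005 sub-protocol defines no AESI for zilucoplan, so no AESI report from the site stands behind the coded search.

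**The concern.** An AESI category exists to gather related preferred terms into one row, so that a signal spread over several terms can be seen. A reader of the hypersensitivity row would expect allergic angioedema or urticaria to be in it, all the more because the row carries the name of a standard query. Zilucoplan is injected subcutaneously every day, which makes a term such as injection site urticaria relevant. If these events are left out of the hypersensitivity row and also miss the anaphylaxis row, the AESI table can show no allergic event in an arm that had some. The serious hypersensitivity row uses the same list and has the same gap.

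**Working it through.** The plan states no figure on this point, so there is none to reproduce. The check compares the lists and then passes example events through the SAP's rules.

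**1. Overlap of the lists (COV-01-005 SAP)**

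- Appendix 2: 10 preferred terms, and 10 of 10 contain the word hypersensitivity.
- Appendix 1, Category A: 11 terms. One, Type I hypersensitivity, is also in Appendix 2.
- Appendix 1, Category C: 29 terms. None is in Appendix 2.
- Terms in this SAP with an explicitly allergic, anaphylactic, angioedema or urticaria name: 5 in Category A, 6 in Category C and 3 in the hepatic list of Appendix 3. That is 5 + 6 + 3 = 14, and 0 of the 14 are in Appendix 2.

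The one shared term shows that the hypersensitivity and anaphylaxis lists were not built as a strict, non-overlapping split.

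**2. Example events under the rules as written**

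| Event as coded | Hypersensitivity row | Anaphylaxis row |
|---|---|---|
| Angioedema alone | no | no |
| Injection site urticaria alone | no | no |
| Urticaria with dyspnoea, inside the window | no | yes |
| Anaphylactic reaction, inside the window | no | yes |
| Either of the last two, two or more days after an injection | no | no |
| Drug hypersensitivity | yes | no |

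The first two lines are the substance of the point. The out-of-window line matters less: with daily dosing it arises mainly after the last injection or after missed doses.

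**3. Size, as an illustration only**

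The documents give no rate for allergic events. Section 16 of the COV-01-005 SAP gives 108 patients randomized. Let r be an assumed proportion of patients with an isolated event such as angioedema or urticaria. The expected number missing from both categories is 108 × r, and the chance that at least one is missing is 1 − (1 − r)^108.

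| Assumed r | Expected patients missing | Chance of at least one |
|---|---|---|
| 1% | 1.1 | 66% |
| 2% | 2.2 | 89% |
| 5% | 5.4 | 99.6% |
| 10% | 10.8 | above 99.9% |

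The rates are assumptions and are not estimates for zilucoplan. The calculation uses all 108 patients. The AESI table uses the safety set, which may be smaller.

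**The case against.** **The comparison does not show that the list departs from the SMQ.** Appendix 1 presents Category C as part of a broad search for signs that may point to anaphylaxis. That broad anaphylaxis terms are absent from a list labelled narrow hypersensitivity does not prove the list wrong. The official content of the narrow query is not in the documents. This stands, and it limits the point to the row as the SAP operates it. For the same reason, a reader might infer an error from the list naming types I, II and IV but not type III. The documents cannot show whether such a term belongs there.

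**The events stay visible.** Master SAP Section 17.1 has all adverse events listed, all treatment-emergent events tabulated by organ class and preferred term, and serious events tabulated and listed. Angioedema would appear there by name and arm. Master SAP Section 17 also excludes statistical comparisons of safety data, and COV-01-005 ended early. All of this stands and keeps the consequence modest. It does not repair the row whose purpose is to collect these terms.

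**The risk difference.** A reader might infer that the AESI risk difference would look falsely clean. The documents do not support that. The only risk difference is for any AESI. That composite also takes in the whole infections class and the long hepatic list of Appendix 3, so many patients with an allergic event may already be counted in it.

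**Anaphylaxis.** A reader might also infer that an anaphylactic reaction is lost. Inside the window it is counted in its own AESI row, and its absence from the hypersensitivity row is then a matter of classification.

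**COV-01-001.** The COV-01-001 SAP prints the same ten terms under "APPENDIX 1 HYPERSENSITIVITY REACTIONS", and a reader might extend the point to it. That does not follow. Section 17.1.1 of that SAP identifies AESIs from investigator reports on the adverse event page. Its sub-protocol asks investigators for diagnoses, or for signs and symptoms, "that are consistent with hypersensitivity reactions, regardless of causality" within 24 hours of dosing. Later reactions are reported only if suspected to be drug-related. An urticaria that the investigator flags is therefore identified by that flag. The SAP does not say what the list is then for, which calls for a sentence of clarification and no change of rule.

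**Conclusion.** The point holds for COV-01-005 only, and for the hypersensitivity and serious hypersensitivity rows of one descriptive table. Under the rules as written, an isolated event coded as angioedema, urticaria, injection site urticaria, allergic oedema or pruritus allergic is absent from both allergy-related AESI categories, and no site AESI report is required as a back-up. Whether any row is in fact under-counted depends on such events occurring, and the size cannot be derived from the documents. In a table of at most 108 patients, one or two missing events would change how the row reads. The any-AESI risk difference is likely to be little affected.

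The conclusion rests on two readings: that Appendix 2 is the operative list for Section 17.1.1, and that coded terms are the only route into these rows. Both follow from the text of that section.

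**What to change.** - **Preferred:** for COV-01-005, run the narrow-scope hypersensitivity SMQ named in Section 17.1.1, in the MedDRA version used for coding, in place of the ten-term list, and state that version.
- **If a custom list is intended:** drop the SMQ label from Section 17.1.1 and Appendix 2. Add the explicitly allergic terms (angioedema, the urticaria terms, allergic oedema, pruritus allergic, and anaphylactic or anaphylactoid reaction), and give the reason for what stays out. Non-specific terms such as shock, oedema, swelling, rash and flushing need not be taken over from Appendix 1.
- **COV-01-001:** leave the identification rule as it is. At most, add a sentence that the Appendix 1 list does not filter out events flagged by the investigator.

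The cost is a revised term list and a program rerun, with no new data collection. The downside is a somewhat larger AESI count, including some events that the drug did not cause.
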